# 12. PHARMACOVIGILANCE

The Investigator is responsible for the detection and documentation of events meeting the criteria and definitions detailed below.

Full details of contraindications and side effects that have been reported following administration of the IMP can be found in the relevant Summary of Product Characteristics (SPC). A specific version (by date) of the SPC will be identified as the source of the RSI, and will be submitted to the PMPB for that purpose.

Participants will be advised to contact their Investigator at any time after consenting to join the trial if any symptoms develop; alternatively participants will be able to report symptoms at their monthly clinic visit. All Serious Adverse Events (SAE) that occur after informed consent until 28 days after delivery of the baby must be recorded and submitted to the regulatory authorities (PMPB) and trial sponsors as soon as possible (within 24-48 hours) after the site becomes aware of the event. In the case of a common AE (known to be caused by Metformin and documented in the SPC) a record of women's experience of these will be collected at each monthly visit.

# 12.1 **DEFINITIONS**

An **adverse event** (AE) is any untoward medical occurrence in a clinical trial participant which does not necessarily have a causal relationship with an investigational medicinal product (IMP).

An **adverse reaction** (AR) is any untoward and unintended response to an IMP which is related to any dose administered to that participant.

A serious adverse event (SAE), serious adverse reaction (SAR). Any AE or AR that at any dose:

• results in death of the clinical trial participant – including neonatal deaths\*\*

- is life threatening\*;
- adverse medicine experience
- requires in-patient hospitalisation^ or prolongation of existing hospitalisation;
- results in persistent or significant disability or incapacity\*\*
- congenital anomaly/birth defect or spontaneous abortion (miscarriage)
- cancer new onset or recurrent \*\*
- Immune Dysfunction: new diagnosis either of HIV or life-threatening immunodeficiency diseases.
- An important medical event, based on appropriate medical judgment that jeopardises the participant and may require intervention to prevent one of the outcomes listed above.

\*Life-threatening in the definition of an SAE or SAR refers to an event where the participant was at risk of death at the time of the event. It does not refer to an event which hypothetically might have caused death if it were more severe.

\*\* Reportable events regardless of the relationship to the IMP.

^Any hospitalisation that was planned prior to enrolment (such as hospitalisation for delivery of the baby) will not meet SAE criteria. Any hospitalisation that is planned post enrolment will meet the SAE criteria.

A suspected unexpected serious adverse reaction (SUSAR) is any AR that is classified as serious and is suspected to be related to the IMP contained in the Reference Safety Information (RSI) for that IMP. The RSI is contained in the Summary of Product Characteristics (SPC) for the IMP, which was submitted to the PMPB as part of the approvals process. The RSI is usually comprised of the 'undesirable effects' detailed in section 4.8 of the SPC; this section is used to assess the expectedness of an SAR.

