# LABOUR and DELIVERY

Admission for delivery will not be a formal study visit and as it is anticipated it will not be recorded as an SAE. Information will be obtained usually from the woman's medical notes on the maternal outcomes of delivery, including method of delivery, indication for delivery method, date and gestation of delivery and blood loss.

Information on the previous 4 weeks' pregnancy and labour and delivery complications will be collected. Adverse events (AE) will be recorded in the patient notes and on the

eCRF. Serious adverse events (SAEs) will be recorded on the SAE form and in the eCRF. All unused study medication returned and sent to pharmacy for recording compliance. The participant diary will be collected and data entered on the eCRF.

The baby outcomes of delivery including baby weight, gender, and birth outcome (e.g. live birth, stillbirth or death in the delivery room) will be collected and recorded by local investigators mainly from hospital notes, and the data will be entered on to the eCRF.

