#### 11.3 STOPPING RULES

We have set the following safety rules for PAPAGENO based on maternal and neonatal deaths that are possibly or definitely related to IMP. We have based these rules on the expected frequency of maternal and neonatal deaths in the population.

Maternal death rate in Malawi is 634 per 100,000 (UNICEF 2015). The combined stillbirth and neonatal death rate in Malawi is 44 per 1000 births (UNICEF 2015). With these expected death rates, we consider that a trebling of this rate would be grounds for serious concern. If such deaths were thought to be related or possibly related to study IMP, that will prompt a halt in recruitment pending review by the independent Data Monitoring and Safety Committee (iDMSC).

Our stopping rules will be based on the number of deaths expected within the first 25, 50 and 100 women recruited. The table below shows the number of expected deaths, and the number within each recruitment band that will trigger a rapid review by the iDMSC. The iDMSC will convene to review data within 14 working days. All the deaths are considered to be related, recruitment will be halted pending the iDMSC. If one or more of the deaths is considered unrelated, recruitment will continue pending review by the iDMSC. Whether or not the deaths are considered related, already recruited to the trial will continue on allocated IMP, pending the iDMSC review. The iDMSC will review unblinded data and advise whether the trial should be stopped, or the circumstances under which the trial should continue.

Number of women recruited	Expected number of maternal deaths	Number of maternal deaths that will trigger a halt to further recruitment.	Expected number of combined stillbirths and neonatal deaths	Number of combined stillbirths and neonatal deaths that will trigger a halt to further
Up to 25	Less than 1 (0.158)	1	1.1	recruitment. 3
Up to 50	Less than 1 (0.317)	1	2.2	6
Up to 100	Less than 1 (0.634)	2	4.4	13

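### Stillbirths count towards the perinatal stopping triggers but are not named as serious adverse events, so prompt reporting with a relatedness judgement is not guaranteed for every event the rule counts

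*Protocol*

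**What the plan says.** **The stopping rule (Protocol 11.3).** The perinatal rule starts from a combined rate: "The combined stillbirth and neonatal death rate in Malawi is 44 per 1000 births". It then sets the level of concern: "we consider that a trebling of this rate would be grounds for serious concern". The table column is headed "Number of combined stillbirths and neonatal deaths that will trigger a halt to further" recruitment, with values 3, 6 and 13 for up to 25, 50 and 100 women. Reaching a trigger calls for review by the independent committee within 14 working days. Recruitment halts pending that review if all the deaths are considered related, and continues if one or more is considered unrelated. The opening sentence of the same section describes the rules more narrowly, as "based on maternal and neonatal deaths that are possibly or definitely related to IMP".

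**The SAE definition (12.1).** The death criterion reads "results in death of the clinical trial participant – including neonatal deaths" and is marked as reportable whatever the relationship to study drug. Congenital anomaly and miscarriage are listed separately. Neither stillbirth nor fetal death is named. A hospital stay for delivery is excluded from the hospitalisation criterion.

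**The reporting clock (12 and 12.6).** SAEs go to the regulator and sponsor within 24-48 hours of site awareness. No other class of event has a clock of this kind.

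**Where stillbirth is named (9.2, Labour and Delivery).** At delivery, "birth outcome (e.g. live birth, stillbirth or death in the delivery room) will be collected", mainly from hospital notes, for entry in the eCRF. No time limit is given, and the delivery admission is not a formal study visit.

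**The exemptions (12.2).** Pregnancy outcomes collected as labour or delivery outcomes are exempted from SAE reporting, followed by an itemised list. Stillbirth is not on the list, but the introductory wording is broad enough to leave its status open.

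**The concern.** A stopping rule that counts events works only if each counted event arrives promptly and carries the information the rule needs. Here that information is the relatedness judgement, because it decides between halting and continuing recruitment. Neonatal deaths are covered: they are SAEs, reportable regardless of relationship, on the 24-48 hour clock. Stillbirths, the other half of the same count, have no stated mandatory route of that kind. The 12.1 list names the losses on either side of stillbirth (miscarriage and neonatal death) and omits the one that 11.3 counts.

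At stake is the timeliness of the trial's only perinatal safety trigger. If a stillbirth sits in the eCRF as a birth outcome, the count may reach 3, 6 or 13 before anyone recognises it. If it has been reached but some of the deaths carry no relatedness judgement, 11.3 does not say whether recruitment halts or continues.

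**Working it through.** **1. Reproduce the table.** Inputs from 11.3: combined rate 0.044 per birth; concern at three times that rate, 0.132. Known multiple pregnancies are excluded (4.3), so births are taken as equal to women.

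| Women | Expected (n × 0.044) | Trebled (n × 0.132) | Stated trigger |
|---|---|---|---|
| 25 | 1.1 | 3.3 | 3 |
| 50 | 2.2 | 6.6 | 6 |
| 100 | 4.4 | 13.2 | 13 |

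The expected numbers match the table, and each trigger is the trebled number rounded down. The triggers are therefore calibrated to a count that includes stillbirths.

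**2. Which events have a mandatory prompt route?**

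| Event | Counted in the 11.3 table | Named in the 12.1 SAE list | 24-48 hour clock |
|---|---|---|---|
| Neonatal death | yes | yes, regardless of relationship | yes |
| Stillbirth | yes | no | only if the site classes it as an SAE |
| Miscarriage | no | yes | yes |

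**3. Chance of reaching each trigger if every event is counted in time.** Exact binomial, P(X ≥ r) with n women and p = 0.132:

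- P(X ≥ 3, n = 25) = 0.659
- P(X ≥ 6, n = 50) = 0.662
- P(X ≥ 13, n = 100) = 0.568

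**4. Worst case: no stillbirth is counted in time.** Let s be the stillbirth share of the combined rate. The protocol gives only the combined rate, so s is an assumption. The counted rate is 0.132 × (1 − s).

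| s | Counted rate | Expected in 100 | P(≥3 of 25) | P(≥6 of 50) | P(≥13 of 100) |
|---|---|---|---|---|---|
| 0 (all counted) | 0.132 | 13.2 | 66% | 66% | 57% |
| 30% | 0.0924 | 9.2 | 41% | 31% | 13% |
| one third | 0.088 | 8.8 | 38% | 28% | 10% |
| one half | 0.066 | 6.6 | 23% | 11% | 1.5% |
| 60% | 0.0528 | 5.3 | 14% | 5% | 0.2% |

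Over the whole range of 30% to 60%, the expected count in 100 women at the trebled rate is well below 13. These figures bound the effect. They do not estimate delay, which the protocol gives no basis for calculating.

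**5. The opening sentence of 11.3 against the rest.** It mentions maternal and neonatal deaths only, while the table counts stillbirths. It refers to possibly or definitely related deaths, while 12.5.2 also has a probably related category and treats all three as adverse reactions.

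**The case against.** The strongest reply is that stillbirths have several ways into the safety data.

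- A stillbirth is plausibly an adverse event. Section 12.2 says doubtful observations are recorded, and 12.3 and 12.4 require a causality assessment for each adverse event.
- The 12.2 exemption is an itemised list without stillbirth on it, and even listed items become SAEs if thought possibly related.
- A site may use the important-medical-event criterion in 12.1.
- Section 7.4 makes fetal death in utero a reason to stop medication, and reasons for stopping are recorded, so an antepartum loss would be visible to the trial team.
- The birth outcome reaches the eCRF, and 9.1 sends interim unblinded outcome data to the monitoring committee.
- Nothing in 11.3 says the count is drawn from SAE forms alone, and the committee's charter, which is not shown, may describe how it is fed.

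Most of this stands. A reader might infer that stillbirths are excluded from safety reporting, that they escape causality assessment altogether, or that the rule would never fire. The documents support none of these: any stillbirth recorded as an adverse event must be assessed for causality, and stillbirths do reach the database.

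What the reply does not supply is a guarantee. The important-medical-event route is a matter of judgement. An adverse event entry that is not classed as serious carries no 24-48 hour clock. Section 9.2 permits entry as a birth outcome without saying that an adverse event record must accompany it. Section 9.1 gives no interval for the interim data.

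The wording gaps in the first sentence of 11.3 are minor taken alone, since the table and the later text make the intention reasonably clear. They are worth correcting in the same edit.

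**Conclusion.** The stopping rule and the reporting rule do not match as written. Section 11.3 counts stillbirths and needs a relatedness judgement for each death; section 12.1 does not name stillbirth among the events that must be reported promptly. The supportable consequence is a trigger recognised late, or reached without the relatedness judgement that decides whether recruitment halts. Permanent loss of the events is not shown.

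The fall from about 57% to between 10% and 1.5% at 13 of 100 women is a worst case. It rests on three assumptions: the true rate is three times the stated 44 per 1000, stillbirths are one third to one half of events, and none is counted in time. The bands at 25 and 50 women move the same way, from 66% to 38-23% and from 66% to 28-11%. It should not be read as the expected performance of the rule.

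The point deserves a correction before recruitment because it concerns participant safety and the remedy is a matter of wording.

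**What to change.** 1. In 12.1, add *stillbirth (fetal death)* to the SAE list, with the existing marker for events reportable regardless of relationship. The 24-48 hour clock and the causality assessment then follow from 12.4 and 12.6 without further text.
2. In 12.2, state that stillbirth is not among the labour and delivery outcomes exempt from SAE reporting.
3. In 11.3, reconcile the first sentence with the section's own table and with 12.5.2 by covering maternal deaths, stillbirths and neonatal deaths, and by including the probably related category.

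**Cost.** A protocol wording change and a few more SAE forms. At the background rate, 4.4 combined events are expected in 100 women; with a stillbirth share of one third to one half (assumption), that is 4.4 × 1/3 ≈ 1.5 to 4.4 × 1/2 = 2.2 extra forms, or about two. The trigger numbers do not change.

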#### 12.2 IDENTIFYING AEs AND SAEs

Participants will be asked about the occurrence of AEs and SAEs at every visit during the study. Open-ended and non-leading verbal questioning of the participant will be used to enquire about AE/SAE occurrence. Participants will also be asked if they have been admitted to hospital, had any accidents, used any new medicines or changed concomitant medication regimens. If there is any doubt as to whether a clinical observation is an AE, the event will be recorded.

AEs and SAEs may also be identified via information from support departments e.g. laboratories.

For this study the following events are NOT considered SAEs as they are expected and are collected as described below in the eCRF. However if the PI or delegate believes any of the events listed below are possibly related to the study treatment then an SAE should be submitted.

- Pregnancy is not considered an AE or SAE, as it is an inclusion criteria.
- Hospitalisations for treatment planned prior to randomisation documented in medical notes and the eCRF prior to randomisation i.e. hospitalisation for elective treatment of a pre-existing condition will not be considered as an SAE. However, *complications occurring during such hospitalisation will be AE/SAEs.*
- Pregnancy outcomes for which data are collected in the eCRF at a study visit or as Labour/Delivery outcomes will also not be reported as SAE are:

- Preterm labour
- Preterm pre-labour spontaneous rupture of membranes
- Preterm delivery in maternal interest
- Preterm delivery in fetal interest
- Hospitalisation for "maternal discomfort"
- Hospitalisation for "rest"
- Hospitalisation for "observation" or "monitoring" for which the women is admitted for a period of less than 12 hours
- Delivery complications such as caesarean section or postpartum haemorrhage
- Admission of the baby to the neonatal unit for any duration

#### 12.3 RECORDING AEs AND SAEs

When an AE/SAE occurs, it is the responsibility of the Principal Investigator, or another suitably qualified physician in the research team who is delegated to record and report AEs/SAEs, to review all documentation (e.g. hospital notes, laboratory and diagnostic reports) related to the event. The Principal Investigator will then record all relevant information in the eCRF/AE log, including in the eCRF SAE section (if the AE meets the criteria of serious).

Information to be collected includes dose, type of event, onset date, Investigator assessment of severity and causality, date of resolution as well as treatment required, investigations needed and outcome. Personal identifying information should be limited to that required by the PMPB, and that required by the Sponsor (which may differ from the PMPB requirements).

#### **12.3.1 Pre-existing Medical Conditions**

Relevant pre-existing medical conditions (i.e. existed prior to informed consent) should be recorded as medical history and only recorded as adverse events if medically judged to have worsened during the study.

#### 12.3.2 Worsening of the Underlying Condition during the Trial

Medical occurrences or symptoms of deterioration that are expected due to the participant's underlying medical condition should be recorded in the Participant's medical notes and only be recorded as an AE or SAE, if medically judged to have unexpectedly worsened during the study. Events that are consistent with the expected progression of the underlying disease should not be recorded as AEs or SAEs..

#### 12.4 ASSESSMENT OF AEs AND SAEs

Each AE must be assessed for seriousness, causality, severity and ARs/SARs must be assessed for expectedness by the Principal Investigator, or another suitably qualified physician in the research team who has been delegated this role, using the Reference Safety Information (RSI; see section 12.1).

For this randomised double blind study, all events and reactions will be assessed as though the participant is taking active IMP (metformin). Potential SUSARs will be unblinded by the Sponsors and both the PMPB and RECs will be informed by the Sponsor if a SUSAR is confirmed. In order to preserve the study blinding, the investigators will not be made aware of SUSAR confirmations.

The Chief Investigator (CI) may not downgrade an event that has been assessed by an Investigator as an SAE, SAR or potential SUSAR, but can upgrade events, if appropriate.

# 12.5 ASSESSMENT OF SERIOUSNESS

The Investigator will make an assessment of seriousness as defined in Section 10.1.

# 12.5.1 Adverse Event Grading

Toxicity grades should be used by the site clinicians and assigned to all SAE:

- 1= Mild
- 2= Moderate
- 3= Severe
- 4 = Life threatening
- 5= death

# 12.5.2 Assessment of Causality

The Investigator will make an assessment of whether the AE/SAE is likely to be related to the IMP according to the definitions below.

- Definitely related
- Probably related
- **Possibly Related:** The nature of the event, the underlying medical condition, concomitant medication or temporal relationship make it possible that the AE has a causal relationship to the study drug. The assessment of causality will be made against the reference safety information found in the reference safety information of the SPC (refer to the appropriate section).

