# • Not related:

Any AE/SAE that is considered to be 'Definitely Related', 'Probably Related', or 'Possibly Related' to the IMP will be deemed an AR or SAR (and, if unexpected, a potential SUSAR) for onward reporting purposes. Only events that are considered to be 'Not Related' to the IMP will be deemed AEs or SAEs

Where non Investigational Medicinal Products (NIMPs) and the AE is considered to be related to an interaction between the IMP and the NIMP, or where the AE might be linked to either the IMP or the NIMP but cannot be clearly attributed to either one of these, the event will be considered as an AR. Alternative causes such as natural history of the underlying disease, other risk factors and the temporal relationship of the event to the treatment should be considered and investigated. The blind should not be broken for the purpose of making this assessment.

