# 12.5.3 Assessment of Expectedness

If the event is an AE the evaluation of expectedness will be made based on knowledge of the reaction and the relevant Reference Safety Information (RSI) information documented in the SPC.

The event may be classed as either:

- **Expected**: the AE is consistent with the undesirable effects of the IMP listed in the RSI (section 4.8 of the SPC).
- **Unexpected**: the AE is not consistent with the known undesirable effects detailed in the RSI

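### Section 12.5.2 ties the causality judgement to the SPC reference safety information, which is the expectedness test, and the SUSAR definition in 12.1 leaves out the condition that the reaction be unexpected

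*Protocol*

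**What the plan says.** **Causality (Protocol 12.5.2).** The site chooses among definitely, probably, possibly and not related. Only 'Possibly Related' carries a description, which begins with ordinary criteria: "The nature of the event, the underlying medical condition, concomitant medication or temporal relationship make it possible that the AE has a causal relationship". The next sentence in the same bullet adds: "The assessment of causality will be made against the reference safety information found in the reference safety information of the SPC".

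**Consequence of the call (12.5.2, under 'Not related').** Anything definitely, probably or possibly related becomes an AR or SAR and, if it is also unexpected, a potential SUSAR. Otherwise: "Only events that are considered to be 'Not Related' to the IMP will be deemed AEs or SAEs". The same text asks for alternative causes, other risk factors and timing to be considered.

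**Expectedness.** Section 12.1 says of section 4.8 of the SPC, which usually makes up the RSI, that "this section is used to assess the expectedness of an SAR". Section 12.5.3 defines an unexpected event as one where "the AE is not consistent with the known undesirable effects detailed in the RSI". On who and what is assessed, 12.4 says "ARs/SARs must be assessed for expectedness by the Principal Investigator" or a delegated physician, using the RSI. Section 12.5.3 instead opens by applying the test to AEs.

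**SUSAR definition (12.1).** A SUSAR "is any AR that is classified as serious and is suspected to be related to the IMP contained in the Reference Safety Information (RSI"). No condition of inconsistency with the RSI follows.

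**Pausing rules (11.3).** These are introduced as resting on "maternal and neonatal deaths that are possibly or definitely related to IMP".

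**The concern.** Relatedness and expectedness are separate questions, and a SUSAR is a serious event that answers yes to the first and no to the second. If one list is consulted for both, an unlisted event looks unrelated and a listed one looks expected. Events that are related but unlisted are the ones the expedited route exists to catch, and the RSI sentence works against recognising them. This matters more here because metformin is used outside its licensed indications (8.1.7), so a pregnancy-specific harm may not be on the list.

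The 12.1 definition fails in the other direction. With no unexpectedness condition, it could lead someone working from that sentence to treat an expected serious reaction as a SUSAR. Under 12.4 the sponsor unblinds potential SUSARs, so some unblinding could be unnecessary.

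Four things depend on the causality call: SUSAR reporting at 7 or 15 days (12.7), the annual report of SARs and SUSARs (12.7), the interim recruitment halt after deaths (11.3), and SAE submission for pregnancy outcomes otherwise exempt (12.2).

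**Working it through.** The point is one of text, so the sections are set side by side first. The only figures nearby are in the 11.3 table.

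**Step 1: what the RSI is used for**

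| Section | Use of the RSI |
|---|---|
| 12.1 | Expectedness of a SAR |
| 12.4 | Expectedness of ARs/SARs |
| 12.5.3 | Expected or unexpected, worded for AEs |
| 12.5.2 | Causality |

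Three sections agree and 12.5.2 is the exception.

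**Step 2: what makes a SUSAR**

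| Section | Serious | Related | Unexpected |
|---|---|---|---|
| 12.1 definition | yes | yes | not stated |
| 12.5.2, under 'Not related' | yes (a SAR) | yes | yes |

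The formal definition and the operating rule disagree on the third condition.

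**Step 3: an unlisted serious event under the RSI sentence**

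1. The site looks for the event in the RSI and does not find it.
2. If the site lets that decide, the event is 'Not related' and remains an SAE (12.5.2).
3. It is then not a potential SUSAR and is not in the annual report (12.7).
4. If it is a death that contributes to a trigger count, 11.3 lets recruitment continue as soon as one of the deaths is considered unrelated.
5. If it is one of the outcomes exempted in 12.2 (for example preterm labour, preterm delivery, postpartum haemorrhage or neonatal unit admission), an SAE is submitted only when the PI or delegate thinks it possibly related. A 'Not related' view leaves it as eCRF outcome data only.

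**Step 4: how sensitive the recruitment halt is**

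The expected counts in 11.3 reproduce as n × rate:
- Maternal deaths at 634 per 100,000: 25 × 0.00634 = 0.1585 (printed as 0.158), 50 × 0.00634 = 0.317, 100 × 0.00634 = 0.634.
- Stillbirths plus neonatal deaths at 44 per 1000: 25 × 0.044 = 1.1, 50 × 0.044 = 2.2, 100 × 0.044 = 4.4.

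The halt needs every one of the k trigger deaths to be considered related. Let q be the chance that one death is so classed. The documents give no value, so a range is assumed, with calls independent between deaths. The chance of a halt once the count is reached is q^k:

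| k (trigger in 11.3) | q = 0.9 | q = 0.75 | q = 0.5 | q = 0 |
|---|---|---|---|---|
| 1 (maternal, up to 25 and up to 50 women) | 90% | 75% | 50% | 0% |
| 2 (maternal, up to 100) | 81% | 56% | 25% | 0% |
| 3 (stillbirth/neonatal, up to 25) | 73% | 42% | 13% | 0% |
| 6 (stillbirth/neonatal, up to 50) | 53% | 18% | 2% | 0% |

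These are illustrations, not estimates. They show that a rule requiring all deaths to be called related loses the halt quickly when the causality text lowers q. At q = 0, where unlisted deaths are always called not related, the halt never occurs.

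**Step 5: what does not depend on the call**

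- All SAEs go to the PMPB and sponsor within 24-48 hours (12, 12.6).
- Deaths, including neonatal deaths, are reportable whatever the causality (12.1).
- Reaching a death count brings unblinded committee review within 14 working days. The relatedness judgement governs only recruitment in the meantime (11.3).
- Any lactic acidosis brings the same review (11.3). Section 8.6 names it as a known complication of metformin, so the lost halt chiefly concerns deaths.

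**The case against.** The strongest reply is that the sections must be read together. Nothing says that an event is related only if it is listed. The operative test in the 'Possibly Related' bullet is clinical, the following text requires alternative causes and timing to be weighed, and 12.5.2 expressly provides for a related event that is unexpected. The term SUSAR itself contains the word, and the 12.1 paragraph goes on to tie SPC section 4.8 to expectedness, so the definition reads like a sentence with words dropped. All events are assessed as if the participant were on metformin, and the Chief Investigator may upgrade but not downgrade (12.4). For the exempt pregnancy outcomes, 12.2 asks for the PI's belief and mentions no list.

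Most of this stands, and it rules out several readings that a reader might infer:

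- *No event can ever be a SUSAR.* This needs the RSI to be the sole causality criterion, which the ordinary criteria in 12.5.2 contradict.
- *Every serious reaction is a SUSAR.* This comes from reading one sentence of 12.1 without 12.4, 12.5.2 or the rest of its own paragraph.
- *An unlisted event is never tested for expectedness.* Section 12.5.3 applies the test to AEs, although SUSAR status still requires relatedness.
- *Such an event disappears from oversight.* SAE reporting and the count-triggered review remain.

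The reply does not remove the sentence directing that causality be assessed against the RSI. It is an instruction, it sits in the only causality category with a description, and it conflicts with three other sections. Nor does it supply the condition missing from 12.1.

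**Conclusion.** The point holds as a contradiction in the safety rules that should be corrected, with limited consequences. Section 12.5.2 assigns the RSI to causality when the rest of section 12 assigns it to expectedness, and the 12.1 SUSAR definition omits a condition that 12.5.2 states.

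What can be lost for an unlisted serious event is:
- SUSAR and annual-report listing
- the interim recruitment halt, when even one trigger death is called unrelated
- possibly, SAE submission for the outcomes exempted in 12.2

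Reporting of SAEs to the PMPB and sponsor and the unblinded committee review are not lost. No endpoint, estimate or planned analysis is affected, so this ranks below a defect that would undermine the trial's conclusions.

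Two assumptions matter. The SPC is not at hand, so whether any particular death or fetal event is unlisted is unknown, and the argument applies to whichever events are. And the effect depends on how far sites let the RSI sentence override the clinical criteria beside it: the text makes misclassification possible, not certain.

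**What to change.** Make three wording changes:

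1. **12.5.2:** delete the sentence that sets causality against the RSI. State that causality is judged on the criteria already named there (nature of the event, underlying condition, concomitant medication, timing and alternative causes), whether or not the event is in the RSI.
2. **12.1:** define a SUSAR as a serious AR that is suspected to be related to the IMP and is not consistent with the RSI.
3. **12.4 and 12.5.3:** reconcile which events are assessed for expectedness, since one names ARs/SARs and the other AEs.

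The cost is a short amendment and a line in site training. No dose, visit or clinical rule changes. The downside is that a few more events may be classed as possibly related, with some added reporting work.
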